8.2.1 Primary Outcome

The primary outcome will be percentage of time in glucose target range, 70 – 180 mg/dl, as determined by CGM on days 3 – 14.

8.2.2 Secondary Outcomes

8.2.2.1 Continuous CGM outcomes for days 3 – 14:

- Key secondary endpoint:
 - Mean CGM glucose
 - Fraction of time spent with CGM glucose <54 mg/dl
- Other secondary endpoints:
 - Fraction of time spent within each of the following glucose ranges:
 - <70 mg/dl
 - >180 mg/dl
 - >250 mg/dl
 - Coefficient of variation
 - Standard deviation

8.2.2.2 Binary CGM outcomes for days 3-14:

- Participants with mean CGM glucose <154 mg/dl (estimated average glucose corresponding to an A1c of 7%)
- Participants with time <54 mg/dl $<1\%$
- Participants with mean CGM glucose ≤ 154 mg/dl and time <54 mg/dl $<1\%$
- Participants with time in range of 70 – 180 mg/dl of $\geq 70\%$

8.2.3 Other outcomes

8.2.3.1 CGM

- Primary and secondary continuous CGM outcomes will additionally be calculated for days 1 – 2
- Primary and secondary continuous CGM outcomes will additionally be calculated for days 3 – 14 for daytime (7 AM to 11 PM) and nighttime (11 PM to 7 AM)
- Binary outcomes
 - Participants with time <70 mg/dl $<4\%$
 - Participants with mean CGM glucose ≤ 154 mg/dl and time <70 mg/dl $<4\%$
 - Fraction of days that CGM was used by participants as part of their usual care
 - Improvement in time 70 – 180 mg/dl by $>10\%$ without an increase in time <54 mg/dl by $>0.5\%$ OR improvement in time < 54 mg/dl by $> 0.5\%$ without a decrease in time 70 – 180 mg/dl by $> 10\%$

8.2.3.2 Non-glycemic

- Continuous outcomes:
 - From bionic pancreas:
 - Mean total daily dose (TDD)
 - Mean daily basal insulin dose
 - Mean daily bolus insulin dose
 - Mean daily correction insulin dose
 - Mean daily dose from meal announcements
 - Fraction of time bionic pancreas disconnected by the participant (self-report on daily questionnaire)

- Number of unscheduled infusion set replacements
- Number of unscheduled Dexcom CGM sensor changes
- In the UC arm:
 - Insulin total daily dose (TDD) for participants using an insulin pump or smart pen
 - Mean daily basal insulin dose
 - Mean daily bolus insulin dose
- In both arms:
 - Number of episodes of symptomatic hypoglycemia per 24 hours (reported daily by participants)
 - Amount of carbohydrate taken to treat or prevent hypoglycemia per 24 hours (reported daily by participants)
 - Change in body weight from baseline
 - Questionnaires scores on each questionnaire that is administered

8.2.3.3 Safety Outcomes

- Episodes of diabetic ketoacidosis
- Episodes of severe hypoglycemia

8.3 Power Analysis

The sample size was selected to detect superiority of the iLet bionic pancreas relative to the comparator group of usual diabetes care based on the primary outcome, percentage time of glucose in target range 70 – 180 mg/dl. The mean and SD of the CGM time in target range for the usual care group was derived from unpublished CGM data in patients with CFRD who wore a blinded CGM for 14 – 28 days. Based on the inclusion criteria of mean glucose ≥ 125 mg/dl (which equates to an expected A1c $> 6\%$), patients had a time in target range of $50 \pm 18\%$ in their usual care. The iLet bionic pancreas is expected to achieve a time in range of $70 \pm 12\%$ based on data from patients in type 1 diabetes. Nine subjects would be required in order to detect a difference between arms using a paired t-test for a power of 80% at an alpha of 5% assuming a correlation pre- and post-treatment of 0.3. We increased the sample size to up to 30 subjects (20 adult subjects and up to 10 pediatric subjects) in order to account for the potential increased variability in glycemic control in response to the bionic pancreas in patients with CFRD, to increase the exposure to the treatment to gather data on safety, and to increase power for detecting differences in secondary outcomes.

9. Risks and Discomforts

Participants may experience mild discomfort associated with the insertion of the infusion sets and the Dexcom sensor. The risk of discomfort due to insertion of infusion sets and sensors may be greater than in their lives outside the trial because it may be more infusion sets and sensors than are used in their usual care.

There is a risk of feeling light-headed from coughing to produce a sputum sample.

There is a risk of hypoglycemia. In the Usual Care arm, this risk is expected to be of the same nature and magnitude as during the participants' lives outside of the trial. In the bionic pancreas arm, this risk is expected to be the same or lower than the risk during the participants' lives outside of the trial based on data from earlier trials. All of the previous studies, albeit in type 1 and type 2 diabetes, have shown that hypoglycemia is similar in the insulin-only configuration of the bionic pancreas when compared with usual care. Based on our experience, we believe that the risk of hypoglycemia will be the same for those with

CFRD.

There is a risk of hyperglycemia. In the Usual Care arm, this risk is expected to be of the same nature and magnitude as during the participants' lives outside of the trial. In the bionic pancreas arm, this risk is expected to be similar to or less than the risk during the participants' lives outside of the trial based on data from earlier trials.

Patients with CF are frequently colonized by resistant strains of bacteria and other infectious organisms. Strict precautions will be taken to minimize the risk of transmission of infectious organisms during the study. In accordance with infection control standards set by the MGH CF Centers, all research staff will be required to utilize contact precautions including gloves and gown when in contact with participants. All rooms, supplies, and equipment will be thoroughly cleaned and disinfected after each use. Additionally, study procedures have been designed to allow for all visits to be completed virtually via videoconferencing systems. Study staff will provide Chromebooks, scales and all study supplies, as well as return shipping materials to facilitate remote visits.

Genetic studies include the risk of loss of confidentiality and risk of emotional distress of learning a new genetic diagnosis. As they are not clinically actionable, genetic data from the sputum microbiome will not be released to the participants. Thus, these risks are small. Therefore, the additional risk from the microbiome analysis is the risk of loss of privacy (discussed below).

10. Potential Benefits

Based on evidence from previous trials of the bionic pancreas, participants enrolled in the study may benefit from a better mean glucose and increased time in the target glucose range without an increase in the risk of hypoglycemia during the bionic pancreas arm.

The data derived from this study will allow us to evaluate the effectiveness of the bionic pancreas control system in use of management of CFRD. Participants will be financially compensated for participating in the study.

11. Data and Safety Monitoring

11.1 Monitoring of Source Data

Data will be captured on case report forms, and any original source documentation will be maintained in the participant's study chart or medical record. During the experiment, Dexcom CGM data will be collected in various ways. Dexcom CGM data will be automatically stored in the bionic pancreas device (from which it will be downloaded at intervals). If the participant uses the Dexcom CLARITY app the CGM data will be wirelessly streamed for storage in the cloud, which will provide redundancy in data capture and mitigate the risk of data loss. Daily emails with a link to a survey will be sent to the participant to document events, including any adverse events, in the previous 24 hours; this data will be captured in REDCap on a MGH server. All of the data will be combined in a single database in the Partners Institutional Lab Archives and will be compared against the primary data files for integrity.

A numeric code will be substituted for the participants personal identifying information in the study database, which will be password protected. The key linking the medical record number of the participant with the numeric code, along with case report forms, and all information that is personally identifiable, will be kept in a locked filing cabinet in an investigator's locked office. All electronic records will be kept in a password protected computer database. All printed computer data will be disposed of confidentially when

no longer needed. Only the study staff will have access to the study database. Participants may not withdraw from the de-identified database, but they may elect to have the key linking their medical record to the de-identified database destroyed.

An audit of procedures, regulatory documentation, and a sample of participant files will be performed by a member of the Diabetes Research Center at least biannually. The audit will be conducted by a staff member who is not directly involved in the conduct of the study. This audit will include a review of regulatory documentation, such as IRB and FDA correspondence, and a review of participant files, including a review of consents, case report forms, and other data from study visits.

All sputum samples will be labeled by study ID number and will be devoid of any identifying information in order to protect patient confidentiality.

The study data may be shared with collaborators at Beta Bionics, but only in a form in which all personally identifiable information has been removed. Shared data will be in the form of a database in which only a number identifies participants.

De-identified data from microbial profiling may be deposited with the National Institutes of Health (NIH) and other central repositories for genomic data. We do not believe that there will be further risks to participants' privacy or confidentiality by sharing this data. There are many safeguards in place to protect participants' information while it is stored and used for research.

Participants may not withdraw their data, as it will be stored in non-personally identifiable form.

11.2 Safety Monitoring and Reporting

This study is considered moderate risk. An external Data and Safety Monitoring Board will oversee the conduct of the study and review its results on a regular basis. The DSMB will be informed if there are any changes to the study protocol that could significantly impact the safety or scientific validity of the study. Additionally, the DSMB will be informed of any severe or unexpected adverse events, including but not limited to any severe hypoglycemia or DKA, within 72 hours. A final DSMB meeting will convene after the completion of the study.

11.2.1 Stopping Rules

The participation of individual participants in the bionic pancreas arm of the study may be discontinued if they experience:

- Diabetic ketoacidosis requiring hospitalization during a bionic pancreas arm
- Seizure or unconsciousness associated with hypoglycemia in a bionic pancreas arm

Unlike in patients with type 1 diabetes, diabetic ketoacidosis (DKA) is very rare in patients with CFRD due to underlying residual beta cell function. However, in the case that a participant experiences one of the above events, the PI will make a determination regarding whether it will be safe to allow them to continue in the study. A participant using the bionic pancreas when they experienced the event will suspend use of the device until a determination is made about the safety of having them continue. If the PI concludes that the event is explainable and unlikely to recur, the participant will be allowed to continue to use the system. Further study participation of an individual participant will be discontinued if they experience more than

one episode of DKA requiring hospitalization, more than one episode of seizure or unconsciousness associated with hypoglycemia, or one of each.

If more than 2 participants must be withdrawn from the study for these reasons, the study will stop and a vote of the DSMB will be required to restart it.

Note that participants may discontinue participation at any time and participants may be removed from the trial for other reasons, for instance failure to comply with study procedures or intercurrent illness that is unrelated to the bionic pancreas but that precludes safe participation. Discontinuation of participation for these reasons will not contribute to a decision to discontinue the trial.

11.2.2 Adverse Event Reporting

11.2.2.1 Definitions

An **adverse event (AE)** is defined as any untoward or unfavorable medical occurrence in a human participant including any abnormal sign (for example, abnormal physical exam or laboratory finding), symptom, or disease, temporally associated with the participant's participation in the research, whether or not considered related to the participant's participation in the research (modified from the definition of adverse events in the 1996 International Conference on Harmonization E-6 Guidelines for Good Clinical Practice).

The PI and co-investigators will review any adverse events to determine severity (serious or non-serious), expectedness (expected or unexpected) and relatedness (related, possibly related or unrelated). The study investigator will assess the relationship of any adverse event to be related or unrelated by determining if there is a reasonable possibility that the adverse event may have been caused by study participation.

To ensure consistency of adverse event causality assessments, investigators should apply the following general guideline when determining whether an adverse event is related:

- **Related:** There is a plausible temporal relationship between the onset of the adverse event and the study intervention, and the adverse event cannot be readily explained by the participant's clinical state, intercurrent illness, or concomitant therapies; and/or the adverse event follows a known pattern of response to the study intervention; and/or the adverse event abates or resolves upon discontinuation of the study intervention or dose reduction and, if applicable, reappears upon re-challenge.
- **Possibly Related:** Possibly related to the research means there is a reasonable possibility that the adverse event, incident, experience or outcome may have been caused by the procedures involved in the research (modified from the definition of associated with use of the drug in FDA regulations at 21 CFR 312.32(a)). Reasonable possibility means that the event is more likely than not related to participation in the research or, in other words, there is a >50% likelihood that the event is related to the research procedures
- **Not Related:** Evidence exists that the adverse event has an etiology other than the study intervention (e.g., preexisting medical condition, underlying disease, intercurrent illness, or concomitant medication); and/or the adverse event has no plausible temporal relationship to study intervention.

The investigator will also classify the event based on expectedness. The event will be classified as **unexpected** if the nature, severity, or frequency of the event is not consistent with known risk information.

Serious adverse event (SAE) means any event temporally associated with the participant's participation in

research that meets any of the following criteria:

- results in death
- is life threatening (places the participant at immediate risk of death from the event as it occurred)
- requires inpatient hospitalization or prolongation of existing hospitalization
- results in a persistent or significant disability/incapacity
- results in a congenital anomaly/birth defect
- any other adverse event that, based upon appropriate medical judgment, may jeopardize the participant's health and may require medical or surgical intervention to prevent one of the outcomes listed above (examples of such events include allergic bronchospasm requiring intensive treatment in the emergency room or at home, blood dyscrasias or convulsions that do not result in inpatient hospitalization, or the development of drug dependency or drug abuse).

Adverse Device Effect (ADE): Any untoward medical occurrence in a study participant which a study device may have caused or to which the device may have contributed.

An event that occurs solely due to participant (i.e., user) error in which the device functions properly generally will not be considered an ADE unless it is determined that the instructions on the screen of the device or user manual (or similar training materials) may have contributed to the event (note: the event may still meet criteria for reporting as an adverse event).

Expected occurrences that will not be documented as an ADE include: CGM tape adherence issues, CGM sensor lasting fewer days than expected per manufacturer, intermittent device component disconnections/communication failures not requiring system replacement or other resolution not described in the user guide, and any device issues clearly addressed in the user guide that do not require additional troubleshooting.

All ADEs, both expected and unexpected will be documented, and reported as an AE when applicable. ADEs, device complaints and device malfunctions will be documented and reported to regulatory bodies as appropriate.

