11.2.2.2 Reporting guidelines

Any serious or unexpected but possibly related adverse events will be communicated to the PI as soon as possible and within 24 hours of the time they are detected. Adverse events and unanticipated problems will be reported to the Partners IRB, the DSMB and Beta Bionics. Reports of adverse events will be made to the FDA in compliance with the terms of IDE.

12. Participant Compensation

Financial compensation will be provided to all participants who complete the screening visit. Participants will be paid \$25 for completing the screening visit whether or not they are eligible to participate in the study.

Study participants will be compensated \$75 for completing each study visit (study start, crossover, and final). The total compensation for a participant who completes the screening visit and scheduled study visits (study start, crossover, and final) would be \$250.

13. References

1. Registry CFFP. Annual Data Report Bethesda, Maryland: Cystic Fibrosis Foundation; 2018.

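### The adverse-event relatedness classes in 11.2.2.1 leave a gap, overlap, and conflict with a two-level rule in the same section, so some uncertain events can miss the 24-hour communication to the PI

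*Combined protocol and SAP*

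**What the plan says.** Section 11.2.2.1 (Definitions) first sets a three-level scale: related, possibly related, unrelated. The next sentence has the investigator "assess the relationship of any adverse event to be related or unrelated", the test being whether there is a reasonable possibility that study participation caused the event. Three definitions follow.

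- *Related* has three limbs joined by and/or: plausible timing where "the adverse event cannot be readily explained by the participant's clinical state, intercurrent illness, or concomitant therapies"; a known pattern of response; or resolution when the intervention is stopped or reduced. None carries a probability threshold.
- The middle class opens with a loose test: "Possibly related to the research means there is a reasonable possibility that the adverse event, incident, experience or outcome may have been caused". The cause in question is the research procedures. The text then sets a threshold, "there is a >50% likelihood that the event is related to the research procedures", by equating reasonable possibility with more likely than not.
- *Not related* has two limbs. One is met when "Evidence exists that the adverse event has an etiology other than the study intervention". The other, enough on its own, is worded "and/or the adverse event has no plausible temporal relationship to study intervention".

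The same section defines an adverse device effect as an occurrence "which a study device may have caused or to which the device may have contributed", with no threshold.

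Section 11.2.2.2 (Reporting guidelines) uses the middle label: "Any serious or unexpected but possibly related adverse events will be communicated to the PI as soon as possible", with a 24-hour limit.

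**The concern.** A *possibly related* class normally holds the events whose cause is uncertain. With a threshold above 50% it no longer does so, because an uncertain event is one that the investigator cannot call more likely than not. *Not related* does not take these events either, unless there is evidence of another cause or the timing is implausible.

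Such cases are foreseeable here. Participants have cystic fibrosis, may continue through illness or a course of oral glucocorticoids (7.7), and may be transplant recipients on steroids or calcineurin inhibitors (7.7.2). A competing explanation will often be available without being shown to be the cause.

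Two things are at stake: whether two investigators following the text would label the same event alike, and whether an uncertain event reaches the PI within 24 hours. Section 8.3 gives safety data as one reason for raising the sample from nine to up to 30, so the causality labels should be usable.

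**Working it through.** The plan states no figure on this point, so the check is one of logic. It takes six yes/no attributes from the definitions in 11.2.2.1:

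- T: timing plausible
- X: readily explained by clinical state, illness or other therapy
- K: known pattern of response
- D: resolves on discontinuation
- G: likelihood above 50%
- E: evidence of another cause

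With and/or read as an inclusive or:

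- Related = (T and not X) or K or D
- Possibly related = G
- Not related = E or not T

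**Admissible patterns.** Six attributes give 2^6 = 64 patterns. I assume that evidence of another cause implies a ready explanation. This removes the 16 patterns with E and not X and leaves 48. Half of these, 24, have likelihood of 50% or less.

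**Coverage of those 24 patterns.**

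- *Not related*: 12 with implausible timing, plus 4 with plausible timing and evidence of another cause = 16.
- *Related*: 18 with K or D, plus 1 with plausible timing, no ready explanation and neither K nor D = 19.
- Both: 16 × 3/4 = 12.
- At least one: 16 + 19 − 12 = 23.
- Neither: 24 − 23 = 1.

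The one uncovered pattern has plausible timing, a ready explanation without evidence for it, no known pattern, no resolution on discontinuation and likelihood of 50% or less. Dropping the assumption about E and X adds 8 patterns at 50% or less. All 8 have E and so meet *not related*; the same single gap remains.

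**Overlap across all 48 patterns.** *Not related* is met by 32 (16 in each half). Only 4 of these lack K, D and G and so meet neither of the other definitions. The remaining 32 − 4 = 28 meet *not related* together with *related* or *possibly related*. An example is an event with evidence of another cause that also resolves on discontinuation.

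These are counts of logical patterns, not event frequencies.

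**Conflict with the two-level sentence.** If reasonable possibility means above 50%, that sentence makes all 24 patterns unrelated. Of these, 24 − 16 = 8 do not meet the definition of *not related*: 19 − 12 = 7 meet *related* only, and 1 is the gap.

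**The 24-hour sentence in 11.2.2.2.** It can be read in two ways.

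| Reading | An uncertain event in the gap that can miss the 24-hour route |
|---|---|
| Serious, or (unexpected but possibly related) | Unexpected and non-serious |
| (Serious or unexpected) but possibly related | Unexpected or serious |

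Taken literally, the sentence names *possibly related* and not *related*, so it also leaves open whether unexpected events classed as *related* are included.

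**Routes that do not use the label.** Reports to the IRB, DSMB and manufacturer (11.2.2.2) and the 72-hour DSMB notice of severe or unexpected events (11.2) carry no relatedness condition. The PI and co-investigators review all adverse events (11.2.2.1). The safety outcomes are episodes of diabetic ketoacidosis and of severe hypoglycemia (8.2.3.3), and the individual stopping rules turn on event type (11.2.1). FDA reporting follows IDE terms that the documents do not give.

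**The case against.** The strongest answer is that the gap is narrow and well protected. *Related* has no threshold, implausible timing alone is enough for *not related*, and the definitions are offered as a general guideline that leaves room for judgement. Uncertain events still reach PI-level review, the IRB, the DSMB and the manufacturer. All adverse device effects are documented under a looser test. Most of this stands, and it limits the consequence to the causality label and the 24-hour communication.

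It also disposes of several stronger readings that a reader might infer:

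- *Every event at 50% or less is unclassified.* It is not: 23 of the 24 patterns meet at least one definition.
- *About half of uncertain events are lost.* That would need both the previous premise and an assumed even spread of likelihoods, and the documents support neither.
- *Device-related harm is undercounted in the device's favour.* The listed safety outcomes and the stopping rules do not filter on relatedness, and section 8 describes no table by relatedness.
- *The adverse device effect definition contradicts the scale.* It concerns the device, whereas *possibly related* concerns research procedures. The different tests can coexist, and the looser one acts as a backstop.

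The objection does not remove the conflict between the two-level sentence and the definitions, or the ambiguity of the 24-hour sentence. The text calls its guideline a means to consistent assessment, and as written it does not achieve that.

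**Conclusion.** The point holds as a defect in the stated rule. Its logical size is one uncovered pattern of 24 at 50% or less, 28 overlapping patterns of 48, and 8 of 24 where the two-level sentence gives unrelated without the definition of *not related* being met. Its practical size is unknown, because the documents give no basis for estimating the share of events. The practical exposure is the causality labels and the 24-hour communication to the PI. The result rests on reading and/or as an inclusive or, on applying the 50% meaning of reasonable possibility to the two-level sentence, and, for the pattern counts but not for the gap itself, on evidence of another cause implying a ready explanation. The change should be made because it is cheap and the affected events are the uncertain ones that the middle class should hold.

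**What to change.** 1. In 11.2.2.1, delete the sentence equating reasonable possibility with a likelihood above 50%.
2. Make *possibly related* the default for any event not clearly *related* or *not related*, including events that meet both definitions. This closes the gap and settles the overlap.
3. Replace the two-level sentence with the three classes, and use them throughout the section and on the case report form.
4. Reword the 24-hour sentence in 11.2.2.2 so that it is clear whether serious events are communicated regardless of relatedness, and that unexpected events classed as *related* are included along with those classed as *possibly related*.

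The cost is protocol and case report form wording, with no effect on design, sample size or treatment. The downside is a few more events classed as *possibly related* and communicated within 24 hours.
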